3.2.4 Follow-up Period

The follow-up period consists of two study visits occurring at Week 12 and Week 16, with visit windows which extend to Study Days 77-98 and 105-126, respectively.

3.2.5 Baseline Value

The baseline value for each assessment will be considered the last non-missing value collected during screening prior to randomization, except for:

- 1) substance use (urine drug screen) which is defined as the first UDS collected during screening, and
- 2) the following assessments which may be collected after randomization and before the first treatment session:
 - Cue Craving Assessment (CCA, first pre-cue, pre-treatment exposure question only)
 - EEG Completion (EEG)

3.2.7 Adverse Event

An adverse event (AE) is any untoward medical occurrence in humans, whether or not considered study device related which occurs during the conduct of a clinical trial. Any change from baseline in clinical status, ECGs, lab results, x-rays, physical examinations, etc., that is considered clinically significant by the site Medical Clinician, is considered an AE.

3.2.8 Suspected Adverse Reaction

A suspected adverse reaction is any adverse event for which there is a reasonable possibility that the study device caused the adverse event. A reasonable possibility implies that there is evidence that the study device caused the event.

3.2.9 Adverse Device Reaction

An adverse device reaction is any adverse event caused by the study device.

3.2.10 Unanticipated Adverse Device Effect

An unanticipated adverse device effect (UADE) is any serious adverse effect on health or safety or any life-threatening problem or death caused by, or associated with, a device, if that effect, problem, or death was not previously identified in nature, severity, or degree of incidence in the investigational plan or application (including a supplementary plan or application), or any other unanticipated serious problem associated with a device that relates to the rights, safety, or welfare of subjects (21 CFR 812.3(s)).

3.2.11 Serious Adverse Event

An adverse event, suspected adverse reaction, or adverse reaction is considered "serious" if, in the view of either the site medical clinician or sponsor, it:

- 1) Results in death: A death occurring during the study, or which comes to the attention of the study staff during the protocol-defined follow-up period, whether or not considered to be caused by the study device, must be reported.

- 2) Is life-threatening: Life-threatening means that the study participant was, in the opinion of the Medical Clinician or sponsor, at immediate risk of death from the reaction as it occurred and required immediate intervention.
- 3) Requires inpatient hospitalization or prolongation of existing hospitalization.
- 4) Results in persistent or significant incapacity or substantial disruption of the ability to conduct normal life functions.
- 5) Involves a congenital abnormality or birth defect.
- 6) Is an important medical event that may not result in one of the above outcomes but may jeopardize the health of the study participant or require medical or surgical intervention to prevent one of the outcomes listed in the above definition of serious event.

3.3 Table, Figures and Listings Conventions

Data for the pre-screened and screened populations will be summarized by site. Data for the ITT population will be summarized by treatment group and overall. Additionally, some analyses for the ITT population will also be summarized by site. For all summaries of ITT population, participants will be analyzed according to the treatment arm to which they were randomized, if applicable, regardless of the subsequent sequence of events regarding study intervention exposure. Analyses summarized by study week will be presented as defined in Section 3.2.2. Analyses for the safety population (defined in Section 3.1.5) will be presented by randomized treatment arm. Data quality, including data audits and protocol deviations, will be summarized by site.

Continuous variables will be summarized using the following descriptive statistics: n (non-missing sample size), mean, standard deviation, percentiles (median, 25th and 75th percentiles, maximum and minimum). Categorical variables will be summarized in terms of frequencies and/or percentages.

4.0 PARTICIPANT ENROLLMENT, DISPOSITION, AND VISIT ATTENDANCE

4.1 Participant Enrollment

The number of participants pre-screened and screened, and the corresponding reasons for ineligibility, will be summarized by site. The number of participants pre-screened by referral source will be presented by eligibility and site, as well as referral source by reason for ineligibility at pre-screening. Note that participants can be pre-screened and screened multiple times. Participants who are pre-screened more than once are not tracked and all pre-screens are summarized. Participants who were screened multiple times will be re-enrolled and their previous Participant ID will be documented on the ENRB eCRF. They will only be considered for the final screening.

The trajectory of actual randomizations versus the expected number of randomizations (according to the first date of randomization and under the assumption that 2.67 participants are expected to be randomized per month per site) along with the proposed number of randomizations will be graphed by site and overall. Proposed versus actual randomizations will be summarized by site in a tabular fashion.

The distribution of treatment assignments by site and strata will be presented.

4.2 Participant Disposition

Participants are defined as study completers if the Week 16 Follow-up Visit is completed as indicated on the Study Completion (STC) form, and they are considered early study terminations if this visit is not completed. Participant disposition will be summarized by site and treatment arm

for the number and proportion of participants completing the study, the number and proportion of participants terminating early from the study, and the reasons for early study termination.

The CONSORT flow diagram will be generated (Moher et al., 2010).

4.3 Visit Attendance

4.3.1 Treatment Period

The treatment period lasts 8 weeks and consists of up to 30 study visits. Additional information about the visit schedule requirements can be found in Section 2.2.3. Due to there being no prespecified expected visit schedule during the treatment period, the Visit Documentation (V08) eCRF is expected at and documents only one visit per study visit week. Visit attendance during the treatment period will be summarized by the minimum number of expected and attended V08-documented visits in the ITT population by study week, site, treatment arm, and primary substance of use.

4.3.2 Follow-up Period

Two visits are expected per participant in follow-up, one visit at Week 12 and one visit at Week 16. The number of expected visits, number of attended visits, and proportion of expected visits attended will be presented by site, treatment arm, and primary substance of use.

4.3.3 Missed Visits

4.3.3.1 Treatment Period

As described above for Treatment Period attendance (4.3.1), only one Visit Documentation (V08) form is expected per week during the 8-week Treatment Period, whether the visit was attended or missed. In the case where a participant does not attend any visits during a treatment period study week, the V08 form is completed to document the reason for a single missed visit for that week. That is, if the target 7-day period is missed, an V08 form is expected to document a missed visit and the next 7-day target period begins.

While there is no schedule for study visits per protocol, participants are encouraged by site staff to create a schedule on the day of randomization and to confirm the schedule for the next visit after each session. The distinction of scheduled visits for documentation purposes pertains only to missed visits. For example:

- If a participant attends a visit, regardless of if it was scheduled or not, the V08 is marked as visit attended.
- If a participant schedules a visit for the following study week and attends, the V08 is marked as visit attended for that study week, regardless of future visits in that study week being attended or missed.
- If a participant schedules a visit for the following study week and does not attend that scheduled visit but does attend another visit in the study week, the V08 is marked as visit attended.
- If a participant schedules a visit for the following study week and does not attend any visits in that period, the V08 is marked as a missed scheduled visit.
- If a participant does not schedule a visit during a study week and misses the entire study week, the V08 is marked as a missed unscheduled visit.

Information on missed visits for the 8 expected treatment period visits (as defined in the MOP, though additional treatment sessions may be completed) will be presented by site, treatment arm, and primary substance of use, including the number of expected visits, number of scheduled

missed visits, number of unscheduled missed visits, the reasons for scheduled visits missed, and the reason for unscheduled visits missed.

4.3.3.2 Follow-up Period

Information on missed visits during the follow-up period will be presented by site, treatment arm, and primary substance of use, including the number of expected visits, number of missed visits, and the reasons for the missed visits. There are two follow-up visits expected per participant during the follow-up period.

5.0 ANALYSIS OF PARTICIPANT BASELINE CHARACTERISTICS

Baseline demographics and characteristics collected on the Demographics (D08) eCRF including sex at birth, age, ethnicity, race, education completed, marital status, employment status, and baseline substance use collected on the Urine Drug Screen (UDS) eCRF (amphetamine, barbiturate, buprenorphine, benzodiazepines, cocaine, ecstasy, fentanyl, marijuana, methadone, methamphetamine, opiates, oxycodone, and phencyclidine) will be summarized by site, primary substance of use, and treatment arm for all randomized participants. Age will be summarized as both a continuous and categorical variable. This table will be repeated by treatment arm for participants who complete the study. Because randomization is expected to produce balance at baseline between the two treatment arms, comparisons of treatment groups with respect to baseline characteristics will be descriptive only. If meaningful differences between treatment arms are suspected, statistical testing may be performed.

6.0 STUDY TREATMENT ADHERENCE

6.1 Early Treatment Terminations

Participants will be considered early treatment terminations as of the date on the End of Treatment (EOT) form. Participants will be considered early treatment terminations if they permanently halt rTMS/sham treatments or fail to complete 20 of the 30 maximum rTMS/sham sessions and do not complete any sessions in Week 8.

The number and proportion of participants terminating treatment early and the reasons for termination will be presented by site, treatment arm, and primary substance of use.

6.2 Treatment Exposure

Participants will receive up to 30 sessions of either active or sham rTMS across the 8-week treatment period. Treatment exposure is captured on the rTMS Intervention (TMS) form and is defined as a performed rTMS intervention. The number of rTMS sessions performed will be summarized as a continuous variable by study visit week, site, and treatment arm for the ITT population, in participants who met the threshold of 20 rTMS sessions, and in participants who had an rTMS session in Week 8.

A summary of engagement in rTMS sessions will also be presented with the number of sessions attended, initiated and stopped prematurely, and performed summarized by treatment arm and primary substance of use. A plot of the average number of rTMS sessions attended by study week and treatment arm will also be provided.

7.0 FEASIBILITY AND EFFICACY ANALYSES

7.1 Definition of the Primary Outcome Measure

The primary (feasibility) outcome measure is the percentage of participants who obtain at least 20 rTMS treatment sessions over the 8-week treatment period. The hypothesis is that at least

75% of participants will receive 20 or more rTMS (active or sham) sessions. The primary outcome measure does not consider whether a participant was randomized with CUD or MUD or randomized to active or sham rTMS treatment arm.

Note that pausing or early termination of an rTMS session is permitted if requested by the participant or if study staff is concerned for participant safety. If less than 50% of any treatment session is completed, the treatment is not considered performed and does not count towards the total count of treatment sessions. That is, a treatment session counts towards the primary outcome measure if it is marked as performed on the rTMS Intervention (TMS) form (TMS.TMPERFM = '1').

In cases where participants received more than 5 treatment sessions per calendar week, over 30 total sessions throughout the treatment, or sessions past Study Day 56 up to the End of Treatment window (Study Day 63), all sessions will still count towards the primary outcome measure.

7.2 Analysis of the Primary Outcome Measure

The primary feasibility outcome will be summarized in the ITT population (defined in Section 3.1.3) by the number of sessions performed per participant, the number of participants with at least 20 sessions, and a 95% confidence interval by the Wilson method. A forest plot of the estimated percentage and confidence interval will also be provided for the primary outcome analysis and supportive analyses listed in Section 7.3, as applicable. The Wilson method was chosen over others, including an exact or Clopper-Pearson method because this method has been shown to have better performance than exact or Wald methods (Brown et al., 2001.). There is no hypothesis testing.

The corresponding SAS code is provided below:

```
proc freq data = data;
  table y / binomial(level = 2 cl = wilson);
run;
```

where:

- data is a dataset with one row per participant, and
- y is the binary variable indicating whether the participant received at least 20 rTMS treatment sessions (y = 1) or not (y=0).

7.3 Supportive Analyses of the Primary Outcome Measure

7.3.1 Demographic Subgroup Analyses

Per NIH policy (NIH, 2016), subgroup analyses will be implemented to assess whether sex at birth (Male, Female), race (Black, White, Other), ethnicity (Hispanic/Latinx, Not Hispanic/Latinx), age (18-44 years, 45 years or greater), and employment status (Employed, Unemployed, Other) are feasibility or effect modifiers. Responses missing, "Don't know," and "Refused to answer" will not be analyzed. The primary outcome percentage will be estimated in each demographic subgroup. Results will be summarized similar to the primary outcome, including a forest plot.

The corresponding SAS code is provided below:

```
proc freq data = data;
  where subgroup = x;
  table y / binomial(level = 2 cl = wilson);
run;
```

where:

- data is a dataset with one row per participant,
- subgroup is the demographic variable of interest,
- x is the subgroup level of interest, and
- y is the binary variable indicating whether the participant received at least 20 rTMS treatment sessions (y = 1) or not (y=0).

7.3.2 Additional Feasibility Analyses

Additional analyses may include estimating the feasibility outcome percentage in the ITT population separately for both CUD and MUD participants, separately for real and sham rTMS, as well as separately for the four combinations of the two factors. A one-sided hypothesis test may be performed using Fisher's exact test at an 0.05 significance level to determine if there are differences in the percentages across or within the factors, though emphasis is placed on estimation and 95% confidence intervals. Summaries of the primary outcome by treatment arm and site and by primary substance of use (cocaine or methamphetamine) will be presented as well as a forest plot. SAS code similar to the demographic subgroup analyses can be used for the confidence intervals. The Fisher's exact test p-value SAS code is provided below:

```
proc freq data = data;
    tables y * x / chisq;
run;
```

where:

- data is a dataset with one row per participant,
- y is the binary variable indicating whether the participant received at least 20 rTMS treatment sessions, and
- x is the binary variable of interest (e.g., treatment arm or SUD).

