15.5 Types of Analyses

15.5.1 Additional Feasibility Analysis

The primary analysis method used for the primary (feasibility) outcome will be completed over all 160 participants. Additional analysis may include estimating the feasibility outcome percentage separately for both CUD and MUD participants, separately for real and sham rTMS, as well as separately for the four combinations of the two factors. Testing may be performed using fisher's exact test at an 0.05 significance level to determine if there are differences in the percentages across or within the factors, though emphasis is placed on estimation and 95% confidence intervals.

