2.2 Study Design and Procedures

2.2.1 Study Design

The study is a randomized, double-blind pilot trial comparing rTMS with sham treatment in reducing stimulant use among individuals with CUD or MUD. Eligible and interested participants will be randomized on a 1:1 ratio to one of two groups; groups will receive up to 30 sessions of active rTMS or sham over the course of an 8-week treatment period.

Four study sites will participate in the study. Each study site will aim to enroll approximately 40 (20 for each of CUD and MUD) participants, with the goal of randomizing 160 (80 for each of CUD and MUD) participants total.

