11.1.1 Results of the Sample Size Re-Estimation

The NIDA CCTN reviewed the sample size re-estimation report issued December 8, 2022 based on database freeze November 9, 2022. The report included the following summaries:

1. Precision Analysis: If the sample size is reduced from $N = 160$ to $N = 120$ under the hypothesized feasibility of 75%, the average halfwidth of the confidence interval would increase by 0.01 or 1% (from .066 to .076). Under the more conservative case of 50% feasibility, the halfwidth would increase by 0.012. From a statistical perspective, the impact of reducing the sample size on precision for the primary outcome is not substantial, though whether this level of precision is acceptable for $N=120$ is largely a scientific question.
2. For a total sample size of 120 and assuming the current observed ratio of methamphetamine use disorder (MUD) to cocaine use disorder (CUD) enrollments continues (i.e., $n=50$ for CUD and $n=70$ for MUD), 80% power is achieved at the observed probability of negative UDS for an effect size of an odds ratio (OR) = 3.0. There is less power to detect smaller treatment effects, though for many of the scenarios considered in the original power calculations this was also the case. While an odds ratio of 2.0 is considered clinically meaningful, this pilot study is not powered for efficacy, so it is not required to detect such an OR of that magnitude.

Following review and feedback from the LN, NIDA CCTN determined the study should continue under the existing protocol as the primary outcome feasibility analysis would not be impacted by any considered change to the sample size. While the study was not powered for the secondary efficacy outcome, it was determined that the investigators should continue recruiting as many participants as possible in the time remaining, given that targeting the clinically meaningful effect size of 2.0 would require a larger sample size to ensure adequate power.

Table 4: Confidence Interval Halfwidth for Primary (Feasibility) Outcome

Feasibility Metric Assumption (%)	Total Sample Size	Average 95% Confidence Interval Halfwidth
50%	40	0.146
	60	0.122
	80	0.106
	100	0.096
	110	0.091
	120	0.088
	130	0.084
	140	0.081
	150	0.079
	160	0.076
	200	0.068
	400	0.049

Table 4: Confidence Interval Halfwidth for Primary (Feasibility) Outcome

Feasibility Metric Assumption (%)	Feasibility Metric Assumption (%)	Feasibility Metric Assumption (%)
60%	40	0.144
	60	0.119
	80	0.104
	100	0.094
	110	0.090

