¹ A rTMS or sham session was considered performed if indicated as such on the rTMS Intervention (TMS) form.

² Percentage is calculated out of the total number of participants randomized.

³ Results are obtained by the Wilson method within the subgroup.

Table 39: Summary of Primary Outcome by Employment Status

Subgroup	Number of Participants Randomized	Number of Sessions Performed Per Participant ¹ Mean (SD)	Results ³		
			Number of Participants with at Least 20 Sessions ^{1,2} N (%)	95% Lower Confidence Limit	95% Lower Confidence Limit
Employed ⁴	N	X.X (X.XX)	N (XX.X%)	XX.XX%	XX.XX%
Unemployed					
Other ⁵					

¹ A rTMS or sham session was considered performed if indicated as such on the rTMS Intervention (TMS) form.

² Percentage is calculated out of the total number of participants randomized.

³ Results are obtained by the Wilson method within the subgroup.

⁴ Employed includes working now, temporarily laid off, sick leave, or maternity leave.

⁵ Other includes retired, disabled (permanently or temporarily), keeping house, student, and other. Missing or refused responses are not included in the analysis (N=X).

Table 40: Summary of Primary Outcome Analysis by Primary Substance of Use

Primary Substance of Use	Number of Participants Randomized	Number of Sessions Performed Per Participant ¹ Mean (SD)	Results ³			
			Number of Participants with at Least 20 Sessions ^{1,2} N (%)	95% Lower Confidence Limit	95% Lower Confidence Limit	p-value
Cocaine	N	X.X (X.XX)	N (XX.X%)	XX.XX%	XX.XX%	0.xxx
Methamphetamine						

¹ A rTMS or sham session was considered performed if indicated as such on the rTMS Intervention (TMS) form.

² Percentage is calculated out of the total number of participants randomized.

³ Confidence limits results are obtained by the Wilson method within the primary substance of use. P-value is obtained from the Fisher's exact test.

Table 41: Summary of Primary Outcome Analysis by Treatment Arm

Treatment Arm	Number of Participants Randomized	Number of Sessions Performed Per Participant ¹ Mean (SD)	Results ³			
			Number of Participants with at Least 20 Sessions ^{1,2} N (%)	95% Lower Confidence Limit	95% Lower Confidence Limit	p-value
Sham	N	X.X (X.XX)	N (XX.X%)	XX.XX%	XX.XX%	0.xxx
rTMS						

¹ A rTMS or sham session was considered performed if indicated as such on the rTMS Intervention (TMS) form.

² Percentage is calculated out of the total number of participants randomized.

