³ Confidence limits results are obtained by the Wilson method within the treatment arm. P-value is obtained from the Fisher's exact test.

Table 42: Summary of Primary Outcome Analysis by Primary Substance of Use and Treatment Arm

Primary Substance of Use	Treatment Arm	Number of Participants Randomized	Number of Sessions Performed Per Participant ¹ Mean (SD)	Results ³		
				Number of Participants with at Least 20 Sessions ^{1,2} N (%)	95% Lower Confidence Limit	95% Lower Confidence Limit
Cocaine	Sham	N	X.X (X.XX)	N (XX.X%)	XX.XX%	XX.XX%
	rTMS					
Methamphetamine	Sham					
	rTMS					

¹ A rTMS or sham session was considered performed if indicated as such on the rTMS Intervention (TMS) form.

² Percentage is calculated out of the total number of participants randomized.

³ Confidence limits results are obtained by the Wilson method within the primary substance of use and treatment arm.

Table 43: Primary Outcome Analysis by Primary Substance of Use and Treatment Arm: Conditional Results

Variable of Interest	Conditional Variable	Results ³	
		Number of Participants with at Least 20 Sessions ^{1,2} N (%)	p-value
Primary Substance of Use: Cocaine	Treatment Arm: Sham	N (XX.X%)	0.xxx
	Treatment Arm: rTMS		
Primary Substance of Use: Methamphetamine	Treatment Arm: Sham		
	Treatment Arm: rTMS		
Treatment Arm: Sham	Primary Substance of Use: Cocaine		
	Primary Substance of Use: Methamphetamine		
Treatment Arm: rTMS	Primary Substance of Use: Cocaine		
	Primary Substance of Use: Methamphetamine		

¹ A rTMS or sham session was considered performed if indicated as such on the rTMS Intervention (TMS) form.

² Percentage is calculated out of the total number of participants randomized.

³ P-value results are obtained from the Fisher's exact test for independence of the outcome and the variable of interest conditional on the given variable.

Table 44: Summary of Primary Outcome Analysis by Site

[figure not shown]
Site	Number of Participants Randomized	Number of Sessions Performed Per Participant ¹ Mean (SD)	Results ³		
			Number of Participants with at Least 20 Sessions ^{1,2} N (%)	95% Lower Confidence Limit	95% Lower Confidence Limit
Site 1	N	X.X (X.XX)	N (XX.X%)	XX.XX%	XX.XX%
Site 2					
Site 3					
Site 4					

¹ A rTMS or sham session was considered performed if indicated as such on the rTMS Intervention (TMS) form.

² Percentage is calculated out of the total number of participants randomized.

³ Results are obtained by the Wilson method within the site.

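### SAP 7.3.2 specifies a one-sided Fisher test for differences by drug and by arm but gives no direction; it should be two-sided

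*SAP*

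**What the plan says.** SAP 7.3.2 lets the analyst estimate the primary feasibility percentage separately for cocaine and methamphetamine participants, for active and sham, and for the four combinations. It then adds: "A one-sided hypothesis test may be performed using Fisher's exact test at an 0.05 significance level to determine if there are differences", across or within these factors. The emphasis, it says, is on estimation and 95% confidence intervals. The SAS code printed there asks for a cross-tabulation with the chisq option and names no tail.

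The same analysis appears in Protocol 15.5.1, with no side given: "Testing may be performed using fisher's exact test at an 0.05 significance level to determine if there are differences in the percentages".

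The table shells in SAP 17.1.5 reserve p-value columns for these tests. The footnotes to Tables 40 and 41 say only "P-value is obtained from the Fisher's exact test". The footnote to Table 43 says "P-value results are obtained from the Fisher's exact test for independence of the outcome and the variable of interest".

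The one hypothesis stated for this outcome is the 75% target. SAP 7.1 says that the outcome measure "does not consider whether a participant was randomized with CUD or MUD or randomized to active or sham rTMS treatment arm". On the primary analysis, SAP 7.2 says: "There is no hypothesis testing".

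**The concern.** A one-sided test asks whether one named group has the higher percentage. A search for differences names no group. The SAP sentence joins the two, so it cannot be carried out until someone decides which tail to use, and the plan does not make that decision.

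Two things are at stake. If a direction is fixed, a difference in the opposite direction will not be found, although the sentence says that differences are sought. If no direction is recorded, the reader of Tables 40, 41 and 43 cannot tell which p-value is printed, and the same data can fall on either side of 0.05.

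**Working it through.** **1. Is there a direction anywhere?**

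| Place | What it gives |
|---|---|
| SAP 7.3.2, text | One-sided, 0.05, differences; no group named as higher |
| SAP 7.3.2, code | No tail selected |
| SAP 7.1 | One pooled target of 75%; drug and arm not ranked |
| SAP Tables 40 and 41 | Fisher's exact test, no tail |
| SAP Table 43 | Test of independence, so non-directional |
| Protocol 15.5.1 | Same test and level, differences, side not stated |
| SAP 7.4 and 9.0 | A directional hypothesis, but for urine drug screens, and tested two-sided |

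None supplies a direction for the feasibility comparison.

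**2. The plan's own figure.** The plan gives no power or sample size for this Fisher test. Its only planning figure for the outcome is the average Wilson half-width in SAP 10.1: 0.066 at N = 160 and a rate of 0.75. Averaging the Wilson half-width exactly over Binomial(160, 0.75) gives 0.0663, so that figure reproduces. The sidedness question does not touch it.

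**3. How much the choice of tail changes one p-value.** Take an illustrative result, not from the documents, of 60/80 against 49/80. The total with at least 20 sessions is 60 + 49 = 109 of 160. With the margins fixed, P(X = x) = C(80, x) · C(80, 109 − x) / C(160, 109).

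- Upper tail, x ≥ 60: 0.0446
- Lower tail, x ≤ 60: 0.9794
- Check: the tails share x = 60, so P(X = 60) = 0.0446 + 0.9794 − 1 = 0.0240
- Two-sided, all tables no more probable than the observed one: 0.0893

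At 0.05 the conclusion changes with the choice of tail.

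**4. Type I error of each reading.** For groups n1 and n2 with a common true rate π, size = Σ Bin(x1; n1, π) · Bin(x2; n2, π), summed over all tables with p ≤ 0.05. The group sizes are assumptions. The SAP 2.2.1 goal gives 80/80, the split considered in SAP 11.1.1 at a total of 120 gives 50/70, and halving 80 gives 40/40 for the within-factor tests of Table 43. At π = 0.75:

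| Groups | Direction fixed in advance | Tail taken from the data | Two-sided |
|---|---|---|---|
| 80/80 | 3.53% | 7.05% | 3.29% |
| 50/70 | 3.15–3.19% | 6.33% | 3.95% |
| 40/40 | 3.06% | 6.11% | 2.87% |

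Over all pairs of group sizes from 50 to 80, at true rates 0.50, 0.60 and 0.75, the ranges are 2.7–4.2% (fixed), 5.7–8.4% (tail from the data) and 2.7–4.9% (two-sided).

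Those rates stop at 0.75, while the hypothesis is at least 75%. At an assumed rate of 0.90 the tail-from-the-data size is 5.54% for 80/80, but 4.87% for 50/50, 4.52% for 50/70 and 3.87% for 40/40. The excess over 5% is therefore not general.

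**5. What a fixed direction misses.** With assumed true rates of 0.75 and 0.60 and 80 per group, power is 0.595 if the direction is right, 0.0001 if it is wrong, and 0.466 for the two-sided test.

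**The case against.** The strongest reply is that nothing here inflates an error rate. One-sided ordinarily means a direction chosen beforehand, and on that reading the size is below 5% in every case in the table. Missing the opposite direction is a property of every one-sided test, not an error in itself. The tests are optional, no decision rule or sample size uses them, and SAP 9.0 plans no further testing of this outcome. Naming a direction would also complete the specification. The word may simply be a drafting slip.

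Most of this stands, and it limits the weight of the point. A reader might infer that the plan runs these tests at 6% to 8%. The documents do not support that: it would need the tail to be picked after seeing the data, which no passage proposes, and even then the size does not always pass 5% at higher true rates.

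The mismatch itself is left. Naming a direction would make the test complete, but the documents give no basis for choosing one, and the result would still not be a test for differences in general. If the word is a slip, it is nevertheless the only statement of sidedness for this test, and an analyst following the SAP would have to apply it.

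**Conclusion.** The specification is wrong as written, with minor impact. SAP 7.3.2 pairs a one-sided test with a non-directional aim and gives no direction, while Protocol 15.5.1 and the Table 43 footnote describe the comparison without one.

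The supported harm is narrow. A fixed direction keeps the size below 5% (3.5% at 80/80 and rate 0.75) but in effect cannot find a difference the other way. With no direction recorded, the printed p-value is ambiguous (0.045, 0.979 or 0.089 in the illustration). A size above 5% (7.1% at 80/80 and rate 0.75) is strictly conditional on a data-chosen tail. Within that condition it holds throughout for groups of 50 to 80 at true rates 0.50, 0.60 and 0.75, but not always above that range.

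These figures rest on the assumed group sizes and rates; the mismatch in wording does not. The primary estimate, its Wilson interval and the secondary analysis are unaffected.

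**What to change.** In SAP 7.3.2, replace one-sided with two-sided, and add a sentence stating that the two-sided Fisher p-value fills Tables 40, 41 and 43. Two-sided fits the stated aim, the protocol and the Table 43 footnote.

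The cost is one word and one sentence, plus a disclosure of timing. SAP 7.10 was written after database lock, and SAP 14.0 dates version 2.0 to 17 January 2025, so any edit now comes after lock and should be dated and labelled as such. The change is conservative in this sense: the two-sided p-value is larger than the one-sided value in the observed direction (0.089 against 0.045 in the illustration). No estimate or confidence interval has to be recomputed.
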